Importantly, CDR3 motifs may be revealed not only at the level of amino acid sequence but also in terms of the biochemical and biophysical properties of the amino acids therein. Taken together, these attributes will be used to examine the clonotypic composition of the naïve and memory CD4 and CD8 T cell pools to determine particular TCR signatures.

TCR sequencing will be performed prior to starting treatment, at count recovery after induction and before consolidation, at 8 weeks after the last round of consolidation, and at 1 year after therapy. Additional blood will not be drawn for this testing.

6.4.6 Cytokine Release Syndrome

We will measure cytokine release with DLI based on peripheral blood analysis. Blood will be taken on the day of cell infusion for both induction and consolidation 2, to be drawn before infusion and 2 days after infusion for both induction and consolidation 2 to evaluate for cytokine release syndrome with DLI. For subjects who do not receive their DLI during induction but rather following consolidation #1 and consolidation #2, blood will be drawn before infusion and 2 days after infusion to measure cytokine release. We will use about 4-8 teaspoons of blood drawn from a vein by a needle-stick or through a central line each time you have these blood tests.

6.4.7 Geriatric evaluation

Comprehensive geriatric assessment: Patients will be required to complete the CGA before induction and 8 weeks after the final round of cellular therapy. We have demonstrated previously that inpatient geriatric assessment and management has positively affected quality of life in the elderly cancer inpatient at no greater length of hospitalization or extra cost than usual care[39]. The CGA has been validated in CALGB studies in elderly patients with solid tumors (breast, colon, prostate cancers)[40]. The mean time to complete the assessment is 23 minutes. Most patients can complete the self-administered portion of the assessment without assistance, and there is no association between age or educational level and the ability to complete the assessment without assistance. Patients may require assistance from the research team for three items: 1) Blessed Orientation- Memory-Concentration (BOMC) test; 2) Timed Up and Go; and 3) Karnofsky performance status (KPS). The remainder of the CGA is either self-administered or administered by a research assistant if the patient requires assistance. The following domains of CGA will be measured: a) Functional Status: Activities of Daily Living, Instrumental Activities of Daily Living, Karnofsky Performance Rating Scale, Timed Up & Go, Number of Falls in Last 6 Months b) Comorbidity: Physical Health Section c) Cognition: Blessed Orientation-Memory-Concentration Test d) Psychological: Hospital

Chemo with Adoptive Haplo DLI

Anxiety and Depression Scale e) Social Functioning: MOS Social Activity Limitations Measure f) Social Support: MOS Social Support Survey: Emotional and Tangible Subscales, Seeman and Berkman Social Ties, and g) Nutrition: Body Mass Index, % Unintentional Weight Loss in the Last 6 Months.

Biologic Markers: Serum concentrations of the candidate cytokines (IL-6, IL-1, IL-2, TNF- α , and CRP) will be determined using Luminex MAP, which facilitates the simultaneous evaluation of multiple immune mediators with advantages of higher throughput, smaller sample volume, and lower cost, when compared to ELISA. All testing will be done in triplicates using the human 29-plex LINCO assay. For RNA extraction, total cellular RNA will be extracted from the leukemic cells using a commercial RNA purification kit; RNA quality will be determined with an A260/A280 ratio and capillary electrophoresis on an Agilent 2100 Bioanalyzer automated analysis system. For DNA microarray analysis, biotinylated cRNA synthesis will be generated with 10 micrograms of total cellular RNA. RNA will be analyzed on the Agilent 2100 Bioanalyzer and then hybridized onto a U133A oligonucleotide array, and thus will be stained, and washed according to an Affymetrix protocol. DNA chips are scanned with the Affymetrix GeneChip scanner, and the signals are processed to evaluate the standard RNA measures of expression. Of note, each gene on this chip is represented by 10 to 20 oligonucleotides, termed a "probe set." The intensity of hybridization of labeled messenger RNA (mRNA) to these sets reflects the level of expression of a particular gene. Samples will be collected before induction, after induction and before consolidation, and at 8 weeks after completing final round of cellular therapy.

Samples will be collected before start of induction and at count recovery prior to consolidation 1.

7.0 EVALUATION CRITERIA AND DEFINITIONS

1. Standardized response criteria will be used following **National Comprehensive Cancer Network (NCCN)** recommendations found on the NCCN website: www.nccn.org.
2. GVHD will be graded with standard criteria (see Appendix II). Other toxicity will be graded as per the NCI Common Terminology Criteria for Adverse Events (CTCAE) version 4.0 (see Appendix III). Grade 3-4 will be reported.
3. Unacceptable toxicity will be defined as either:
 - a. Grade III or IV aGVHD of the gut or liver or Grade IV aGVHD of the skin lasting > 7 days;

Chemo with Adoptive Haplo DLI

- b. Other grade IV CTCAE toxicity attributable to the DLI (e.g. infusion reaction, and distinct from grade IV toxicity attributable to chemotherapy) and lasting > 7 days
 - c. Treatment-related mortality (TRM), keeping in mind that anticipated mortality from standard induction chemotherapy in the elderly ranges from 11% for subjects 55-65 years-old with ECOG 0 to 50% for subjects older than 75 years with ECOG 2 [1].
4. Disease-free survival (DFS) is the time from CR to relapse or death.
5. Overall survival (OS) is the time from start of therapy to either death or the last day of follow-up for that patient.
6. Event Free Survival (EFS) is the time from start of therapy to progression of AML or relapse or death.
7. Neutrophil recovery time is defined as the first of 3 consecutive days in which the ANC is $>0.5 \times 10^9/L$
8. Platelet recovery is defined as the first of 3 consecutive days in which the platelet count is $>20 \times 10^9/L$
9. PD1/PDL1/PDL2 expression (marker of T cell exhaustion)
- 10.

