5.1 Patient Eligibility

1. Subjects must have their diagnosis of high-risk AML or high-risk MDS confirmed by pathologic review of bone marrow biopsy according to WHO guidelines [35] (see below for definitions of high-risk)
 - We will define patients as high risk AML and thus eligible if they meet one or more of the following criteria:
 - a. Secondary AML (from underlying MDS or therapy related)
 - b. Presence of complex cytogenetic abnormalities (≥ 3 cytogenetic abnormalities), all monosomies, del 5q, del 7q, inv3, t(3;3), t(6;9), t(9;22), abn 11q23 (excluding t(9;11))[36]
 - c. FLT3-ITD mutation positive
 - d. Age ≥ 65 years given poor outcomes even with favorable

Chemo with Adoptive Haplo DLI

cytogenetics[1]

- We will define subjects as high risk MDS and thus eligible if they have a MD Anderson Comprehensive Cancer MDS Risk Score ≥ 9 [3]
- 2. Subjects must have ECOG Performance status of 0,1,or 2; if ECOG 2, they must also have a Charlson comorbidity index of ≤ 5 .[37]
- 3. Subjects must be ≥ 55 years of age
- 4. Subjects should have a potential 3-5/6 HLA-matched related haploidentical donor that will be evaluated for eligibility to provide DLI.
- 5. Patient should be able to provide informed consent
- 6. Subjects must have a MUGA and /or ECHO or cardiac MR. The required minimum standards include MUGA or ECHO or cardiac MR showing an EF of 40%. Those with an EF 40-49% must also have a cardiologist consult and assist with management.
- 7. PFTs with DLCO are conditional for subjects at the discretion of the physician. The required minimum standards for those who have PFTs include DLCO of 40%. Those with DLCO of 40-49% must have a pulmonologist consult and assist with management.
- 8. Subjects of all genders and races are eligible

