6.3 Treatment Plan

6.3.1 Induction therapy

Eligible subjects will receive induction chemotherapy with idarubicin (12 mg/m^2 intravenously for 3 days) and cytarabine (100 mg/m^2 intravenously for 7 days) starting Day 1 and ending Day 7 as described in Figure 1. Patients 80 years or older may receive 2 and 5 days of idarubicin and cytarabine respectively starting Day 1 and ending Day 5 (optional, at physician discretion). HLA-mismatched DLI will be administered Day 9

Chemo with Adoptive Haplo DLI

(DLI will occur on Day 7 for 5+2 regimen), approximately 24-48 hours following completion of chemotherapy at a dose of 1×10^8 CD3+ cells; however, due to logistics of planning infusions with staffing, donor availability, weekends/holidays, etc., it may be necessary to postpone cell infusion up to 96 hours, which will be allowed without being considered a protocol violation.

Subjects who experience no remission or partial remission will receive a second course of the identical induction chemotherapy (IND2). IND2 should include 7+3+DLI as per IND1, but if cells are not available as per 6.2.3, chemotherapy alone can be given without being considered a protocol violation.

Given the time constraints presented by the need to start induction chemotherapy as soon as possible, in some cases, it may not be logistically possible to administer cells with induction (e.g., obtaining insurance approval for clinical trial/DLI may take a while, and approval may not be back in time for a patient to receive cells). In these cases, patients would just receive standard induction chemotherapy and cells would be administered after CON1 in addition to CON2 (see below). Timing of correlative laboratory studies will be adjusted to match cell infusion. Guo et al. have reported improved outcomes with high cell doses (1×10^8 CD3+ cells/kg) administered after consolidation, even in patients who receive standard induction chemotherapy without cells.¹

¹Guo M, Hu KX, Liu GX, Yu CL, Qiao JH, Sun QY, Qiao JX, Dong Z, Sun WJ, Sun XD, Zuo HL, Man QH, Liu ZQ, Liu TQ, Zhao HX, Huang YJ, Wei L, Liu B, Wang J, Shen XL, Ai HS. HLA-mismatched stem-cell microtransplantation as postremission therapy for acute myeloid leukemia: long-term follow-up. *J Clin Oncol.* 2012 Nov 20;30(33):4084-90. doi: 10.1200/JCO.2012.42.0281. Epub 2012 Oct 8.

[figure not shown]

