6.4.2 Laboratory and other testing

(Correlative Studies for 00043247 v. 15.06.19 Lab Manual)

Evaluation for supportive care during therapy/recovery and after therapy will be as follows (Recommended but may change based on clinical status per treating physician):

- (a) CBC will be obtained daily during induction until transfusions of platelets and red blood cells are not regularly required, then as clinically indicated. When the white count reaches greater than

Chemo with Adoptive Haplo DLI

500/uL, then add differential and follow to document when ANC > 1,500/uL. After consolidation, CBC and differential will be checked every 2 weeks or as clinically indicated.

- (b) Serum chemistries and liver functioning tests at least weekly and as clinically indicated while during therapy/recovery; chemistries and liver function tests will also be checked at 8 weeks and then every 3 months for 2 years.
- (c) Serum quantitative beta-HCG will be checked one week prior to induction in females.
- (d) Biopsies of organs suspected to be involved with GVHD as clinically indicated (e.g., skin, liver, GI tract).
- (e) Chest X-ray as clinically indicated.
- (f) Bone marrow biopsy at Day 14 (per investigator discretion) as well as after count recovery (mandatory)
- (g) HLA Antibodies at count recovery and 8 weeks after CON2.
- (h) For patients who relapse or have refractory disease going off study, collect the following labs: peripheral blood for minimal residual disease testing, NK lysis assay, microchimerism, TCR sequencing, PD1/PDL1/PDL2 expression.

6.4.3 Detection of donor chimerism and microchimerism:

Hematopoietic donor chimerism will be assessed in all subjects with the use of standard cytogenetic and semiquantitative PCR-based analysis of short tandem repeats with 1% sensitivity.

Microchimerism will be analyzed using real time PCR (qPCR) at a sensitivity of 1/100,000.

These assays will be performed at count recovery prior to each new cycle of therapy, at 8 weeks after the last round of consolidation, and if still positive, every 3 months after completing therapy for up to two years. Additionally, in the case of mother-child pairs or sibling pairs that are mismatched in NIMA, this will be conducted before first infusion to assess for persistent maternal-fetal microchimerism.

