11.2.3 Evaluate efficacy with respect to disease response and survival.

Additional efficacy endpoints include response rate, DFS, EFS, and OS. The response rate will be calculated with one sided 85%

Chemo with Adoptive Haplo DLI

confidence interval. DFS, EFS, and OS will be estimated using the method of Kaplan and Meier.

11.2.4 Evaluate immune recovery.

Immune reconstitution results will be tabulated and recorded. For the evaluation of recovery of immune function post-engraftment, we will use descriptive statistics of cytokine profiles, lymphocyte and NK enumeration and flow-based assays and make patient-specific plots of immune function parameters across time. These measurements will be performed prior to induction, prior to each round of consolidation, 8 weeks after the last cycle of consolidation, and every 3 months after treatment for up to 2 years. Specifically, we will:

1. monitor leukocyte subsets using flow cytometry:
 - CD3+
 - CD4+
 - CD8+
 - regulatory (CD4+, CD25+, CD62L+)
 - cytotoxic/late memory (CD8+, CD57+, CD28-) and activated (CD8+, HLADR+) T cells
 - naïve CD4+ T cells with L-selectin expression (CD4+, CD45RA+/CD45RO-, CD62L+)
 - gamma-delta T cells
 - B cells (CD19+, CD3-, CD16-, CD56-)
 - natural killer cells (NK) (CD3-, CD16+/CD56+, CD107+)
 - natural killer T cells (NKT) (CD3+, CD16+/CD56+, CD107+),
 - plasmacytoid dendritic cells (DCs) (CD123+, CD11c-)
 - myeloid DCs (CD123-, CD11c+)
2. quantify recent thymic immigrants by the presence of TCR rearrangement excision circles (TREC) performed by real-time quantitative-PCR of DNA collected from an isolated fraction of CD31 T cells
3. perform next generation sequencing of TCR gene rearrangements to analyze diversity in the TCR repertoires produced by the rearrangements of the variable region genes.
4. in vitro assays of NK function (measure CD16 expression, intracellular CD107a degranulation and cytokine secretions of IFN γ and TNF α after 4 hour co-culture with an effector:target ratio of 2:1)
5. measure immunoglobulin levels as a function of B-cell activity and recovery

Chemo with Adoptive Haplo DLI

6. measure cytokine levels, particularly IL1, IL1-beta, IL2, IL6, IL8, IL15, IL21, IFN-gamma, TNF-alpha, TGF-beta, CRP
7. microchimerism monitoring to determine the level of donor cells (as well as the presence of any pre-existing maternal-fetal microchimerism)
8. KIR typing to determine the effect of KIR ligand mismatch
9. PD1/PDL1/PDL2 expression (marker of T cell exhaustion)

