| PD1/PDL1/PDL2 expression (Research) | X | | X | At 8 weeks after last therapy | X |
| Cytokine Release Syndrome (Research) | | To be drawn before infusion and 2 days after infusion for IND1, IND2, and CON2 as applicable | | | |
| Toxicity monitoring (Grade 3-4) (Epic) | | Daily | Qo wk | Qo wk till 8 weeks after last therapy and then q 4 weeks for 12 more weeks | |
| Acute GVHD monitoring (Epic) | | Daily | Qo wk | Qo wk till 8 weeks after last therapy and then q 4 weeks for 12 more weeks | |

¹ Tests at entry are recommended to be done within 1 week before initiating therapy; however if there are no sig. change in patient's status and tests are less than 4 weeks old then they are acceptable; exceptions include bone marrow aspirate and biopsy and cardiopulmonary testing (acceptable if within 8 weeks)

² Therapy and recovery refer to the period while the patient is receiving induction (IND1 or IND2) or consolidation chemotherapy until count recovery and discharge

³ For cardiopulmonary testing, refer to section 5.1.

⁴If patient already had a bone marrow biopsy and this was not collected, ok to skip

⁵ Per investigator discretion

⁶ Count Recovery would be considered when the ANC count is >1000/uL

⁷ If any subjects do not complete all the therapies (i.e. Induction 1/2, Consolidation 1 and 2), they will be followed for survival, but do not need to complete any listed assessments

⁸Any leftover cells at q3months after completing therapy will be used to run NK Lysis, TCR sequencing, and PD1/PDL1/PDL2 expression research samples. Additional blood will not be drawn for this testing.

*Other labs may be performed/followed per institutional policy

II. DONOR SCHEDULE OF EVENTS TABLE

| Test | At Entry |
|---|----------|
| History, physical (Epic) | X |
| ABC / DIFF, Serum BUN/Cr/CA/MG/PO/AST/ALT/Bili/TP/ALB/K/NA /CL/CO3/Glu/CMV viral titre (Epic) | X |
| Serum quantitative Beta-HCG for females (Epic) | X |
| CXR (AP/lateral), EKG (12 lead) (Epic) | X |
| FACT labs* (Epic) | X |
| KIR typing (Research) | X |
| Microchimerism (Research) | |
| TCR sequencing (Research) | X |

*See appendix for standard FACT (Foundation for Accreditation of Cellular Therapy) labs. FACT labs must be drawn and final test results available within 7 days prior to infusion into the patient.

III. GVHD Grading Criteria

| GvHD | | | | | | |
|--------------------|----------------------------------|----------|--|--|-------------------------------|---|

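### The EFS definition counts progression of AML but not of MDS, although high-risk MDS subjects are enrolled and share the same EFS curve

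*Combined protocol and SAP*

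**What the plan says.** The only definition of EFS is in section 7.0 item 6: "Event Free Survival (EFS) is the time from start of therapy to progression of AML or relapse or death". Eligibility is wider than AML. Section 5.1 begins: "Subjects must have their diagnosis of high-risk AML or high-risk MDS confirmed by pathologic review of bone marrow biopsy".

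Section 11.2.3 states "Additional efficacy endpoints include response rate, DFS, EFS, and OS" and "DFS, EFS, and OS will be estimated using the method of Kaplan and Meier". It does not separate AML from MDS, and it adds no further event and no censoring rule.

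Two other places bear on what gets recorded. Section 6.4.2(f) makes a marrow examination after count recovery mandatory. Appendix I, footnote 7, says of subjects who do not complete all therapies that "they will be followed for survival, but do not need to complete any listed assessments".

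**The concern.** The progression part of the definition names one of the two enrolled diseases. If the rule is followed as written, progression of MDS that stops short of AML is not an event. The same clinical course then ends EFS for an AML subject and leaves an MDS subject event-free.

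The omission can only delay or remove events, so it pushes EFS up. The pooled curve would also depend on the mix of AML and MDS enrolled.

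This has some weight because DFS cannot fill the gap. Item 4 of the same section says "Disease-free survival (DFS) is the time from CR to relapse or death", so DFS leaves out everyone who never reaches CR. EFS is the planned time-to-event measure of disease control that starts at treatment and covers all subjects.

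**Working it through.** The documents give no EFS rate, event count or power, so there is no figure to reproduce. The check sets out the event rule by clinical course and then sizes the affected group.

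**1. Which courses end EFS under item 6**

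| Course | AML subject | MDS subject |
|---|---|---|
| CR, then recurrence | event (relapse) | event (relapse) |
| No CR, disease progresses | event | no event, unless the disease has become AML (arguable) |
| No CR, disease persists without progressing | no listed event | no listed event |
| Death | event | event |

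Only the second row treats the two diseases differently. The third row is a separate, secondary matter (step 4).

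**2. How many subjects are at risk of the MDS gap**

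Inputs: 21 evaluable subjects at most (section 11.1); CR rates of 80% and 42.8% in the two arms of the pilot study in section 3.7. The MDS share is not given in the documents; 20–40% is assumed. The pilot study was in AML, so using its CR rates for MDS is also an assumption.

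Formula: 21 × MDS share × (1 − CR rate).

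- Low end: 21 × 0.20 = 4.2 MDS subjects; 4.2 × (1 − 0.80) = 0.8.
- High end: 21 × 0.40 = 8.4 MDS subjects; 8.4 × (1 − 0.428) = 4.8.

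So about 1 to 5 MDS subjects would not reach CR. At the lowest CR rate in section 3.1 (30%), the high end is 8.4 × 0.70 = 5.9.

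**3. Ceiling on the effect on the pooled curve**

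The gap raises EFS only through subjects who have progressed and are still alive. Assume complete follow-up to one year, and that 10–50% of the step 2 subjects are alive then, all with uncounted progression. The excess in one-year EFS is MDS share × (1 − CR rate) × proportion alive.

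- Low: 0.20 × 0.20 × 0.10 = 0.004.
- High: 0.40 × 0.572 × 0.50 = 0.114.

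That is under 1 to about 11 percentage points. It is an upper limit, because some of those alive would not have progressed.

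**4. Secondary: no CR after the last induction course**

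- At CR 80%: 21 × 0.20 = 4.2 subjects.
- At CR 42.8%: 21 × 0.572 = 12.0 subjects.

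The 1 to 5 MDS subjects in step 2 lie inside this group and must not be added to it.

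To show how far the convention matters, assume one-year DFS of 45% among CR subjects (the alternative in section 11.1.2) and 10–50% of the others alive at one year with no counted progression. Ignore the time taken to reach CR. One-year EFS is CR × 0.45 if failure counts as an event, and at most CR × 0.45 + (1 − CR) × proportion alive as written.

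- CR 80%: 0.36, against up to 0.38–0.46.
- CR 42.8%: 0.19, against up to 0.25–0.48.

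**The case against.** The strongest reply is that little turns on this. EFS is not in the primary objectives. It is not named in secondary objective 2.2.3, which lists CR and OS. It has no test, target rate, power or stopping role. That stands, and it limits the point to a minor one. It does not reconcile section 5.1 with section 7.0.

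Four stronger readings are tempting, and the documents do not support them.

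- **EFS counts nothing but AML progression.** Relapse and death count for every subject, and an MDS subject whose disease becomes AML arguably has an event.
- **All 4 to 8 assumed MDS subjects have uncounted progression.** That is simply the assumed number with MDS. Those who reach CR and recur have an event. Only those without CR who progress while alive are affected.
- **EFS becomes OS for subjects who fail induction.** AML progression seen at the mandatory count-recovery marrow, or before a subject leaves the study, is still an event. Footnote 7 limits later assessment but does not erase what was already seen. The supportable statement is that death may be the only later event captured.
- **Leaving out induction failure is an error.** The protocol recognises the state: section 6.4.2(h) begins "For patients who relapse or have refractory disease going off study, collect the following labs", naming refractory disease apart from relapse. But no section requires it to be an EFS event, so this is a convention left unstated. An investigator might call some refractory AML progression; the text does not say either way.

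**Conclusion.** The point holds as a minor error in a secondary, descriptive endpoint. The progression component of EFS does not fit the enrolled population: MDS progression short of AML is not an event, so the two diseases are measured on different event sets. EFS is biased upward for MDS relative to a rule that counts progression of either disease.

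About 1 to 5 of 21 subjects are at risk. This rests on the assumed 20–40% MDS share and on AML-based CR rates carried over to MDS. Not all of these subjects will progress while alive. The mismatch itself rests on no assumption, because it follows from reading sections 5.1, 7.0 and 11.2.3 together.

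The handling of induction failure (about 4 to 12 of 21 at the same CR rates) is a secondary gap in specification. DFS, CR, OS and the safety rule are not affected.

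**What to change.** In section 7.0 item 6, define EFS as running from start of therapy to the earliest of progression of AML or MDS, relapse, or death. This changes a few words, and EFS becomes slightly less favourable. It is needed whichever convention is chosen for induction failure.

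In the same item, state whether failure to reach CR after the last induction course is an event and, if so, on what date. The count-recovery marrow in section 6.4.2(f) is already mandatory, so dating it needs no new test. Counting failure would lower EFS further; not counting it is acceptable if stated.

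The new wording cannot by itself capture progression that nobody looks for. Section 11.2.3 should therefore say how progression is recorded, or EFS censored, once a subject falls under footnote 7 of Appendix I. A stated censoring rule costs only text; further data collection would cost more.
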